2.1.4 Safety endpoints

The primary endpoint of this study is the number (n) and percentage (%) of patients experiencing any treatment-emergent adverse events (TEAE). Adverse events (AEs), serious adverse events (SAE), adverse events of special interest (AESI), adverse events leading to treatment discontinuation are collected at each visit from the time of informed consent signature to the end of study. The safety analysis will be based on the reported adverse events and other safety information, such as clinical laboratory data, vital signs, ECG and physical examination.

Generally, for scheduled on-site safety assessments, including laboratory, vital sign, ECG, physical examination, all data collected in the study regardless of the dose regimen will be included for the full analysis set. For the modified analysis set, data collected on or after the day of the first IMP of 300 mg q4w will be censored for patients who will be exposed to 300 mg q4w regimen in LTS14424 study. Particularly, all data from patients with initial dosage as 300 mg q4w will be excluded from the modified analysis set.

2.1.4.1 Adverse events variables

Adverse event observation period

- Pre-treatment adverse events are adverse events that developed or worsened or became serious during the pre-treatment adverse event period.
- Treatment-emergent adverse events are adverse events that developed or worsened or became serious during the treatment-emergent adverse event period.
- Post-treatment adverse events are adverse events that developed or worsened or became serious during the post-treatment adverse event period.

Pre-treatment, treatment-emergent, and post-treatment emergent adverse event periods are defined in [Section 2](#).

All adverse events (including serious adverse events and adverse events of special interest) will be coded to a lower-level term (LLT), preferred term (PT), high-level term (HLT), high-level group term (HLGT), and associated primary system organ class (SOC) using the version of Medical Dictionary for Regulatory Activities (MedDRA) currently in effect at Sanofi at the time of database lock.

Adverse events of special interest (AESI) and other selected AE groupings will be searched based on the same criteria used in the parent study ([Table 4](#)).

Table 4 - Criteria for adverse events of special interest and other selected AE groupings

| AE Grouping | Criteria |
|---------------------------------------------------------------------------------------------------|-------------------------------------------------------------------------------------------------------------------------------------------------------------------------------------------------------------------------------------------------------------------------------------------------------------------------------------------------------------------|
| AESI | |
| Anaphylactic reaction | Anaphylactic reaction algorithmic approach (Introductory Guide for Standardised MedDRA Queries (SMQs) Version 18.1): includes anaphylactic reaction narrow SMQ (20000021) terms; for selection based on occurrence of multiple symptoms, the symptoms must have occurred within 24 hours of each other, which are related to IMP and requires treatments |
| Hypersensitivity (medically reviewed) | Hypersensitivity narrow SMQ (20000214) and [AE corrective treatment/therapy='Y' or Action taken with IMP='Drug withdrawn' or Action taken with IMP='Drug interrupted'] followed by medical review (documented process) for selection of relevant systemic hypersensitivity events |
| Severe injection site reactions that last longer than 24 hours or serious injection site reaction | HLT = 'Injection site reaction' and either with serious status, or with severe status and (AE end date/time -AE start date/time) \geq 24 hours or ongoing |
| Severe or serious infection | Primary SOC = 'infections and infestations' and with severe or serious status |
| Parasitic infection | The Infection Type 'Parasitic' was checked on the eCRF page "Infection Event Form" |
| Opportunistic infection | The question "Has the AE been assessed as opportunistic infection?" is answered "Yes" on the eCRF page "Infection Event Form" |
| Drug-related hepatic disorder | Drug-related hepatic disorders - Comprehensive search narrow SMQ (20000006) |
| Pregnancy | Primary SOC = 'Pregnancy, puerperium and perinatal conditions', or PT in (Aborted pregnancy, False negative pregnancy test, Pregnancy test positive, Pregnancy test urine positive, Ectopic pregnancy termination) |
| Symptomatic overdose with IMP | The question "Is the event a Symptomatic Overdose with IMP?" is answered "Yes" on the eCRF page "Adverse Event" |
| Symptomatic overdose with noninvestigational medicinal product (NIMP) | The question "Is the event a Symptomatic Overdose with non-IMP?" is answered "Yes" on the eCRF page "Adverse Event" |
| Other selected AE grouping | |
| Injection site reaction | HLT = 'Injection site reaction' |
| Malignancy | Sub-SMQ (20000091) - Malignant or unspecified tumors |
| Partner pregnancy | PT in (Pregnancy of partner, Miscarriage of partner) |

| AE Grouping | Criteria |
|-------------------------|--------------------------------------------------------------------------------------------------------------------------------------------------------------------------------------------------------------------------------------------------------------------------------------------------------------------------------|
| Conjunctivitis (narrow) | PT in (Conjunctivitis, Conjunctivitis allergic, Conjunctivitis bacterial, Conjunctivitis viral, Atopic keratoconjunctivitis) |
| Conjunctivitis (broad) | PT in (Conjunctivitis, Conjunctivitis allergic, Conjunctivitis bacterial, Conjunctivitis viral, Atopic keratoconjunctivitis, Blepharitis, Dry eye, Eye irritation, Eye pruritus, Lacrimation increased, Eye discharge, Foreign body sensation in eyes, Photophobia, Xerophthalmia, Ocular hyperaemia, Conjunctival hyperaemia) |
| Eosinophilia | HLT = 'Eosinophilic disorders' or PT = 'Eosinophil count increased' |

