9 ASSESSMENT OF INVESTIGATIONAL MEDICINAL PRODUCT

9.1 PRIMARY ENDPOINT

The primary endpoint for this study is the number (n) and percentage (%) of patients experiencing any TEAE (definition see [Section 10.4.1.1](#)) during total study periods.

Additional analyses will describe the number (n) and percentage (%) of patients experiencing any:

- Serious adverse events (SAE) (SAE definition refers to [Section 10.4.1.2](#)).
- Adverse events of special interest (AESI) (AESI definition refers to [Section 10.4.1.3](#)).
- Adverse events related to IMP.
- Adverse events leading to permanent IMP discontinuation.
- Adverse events other than ISR.

Adverse events, including SAEs and AESI, will be collected at any time during study starting from signed consent form. Any new AEs (including worsening AEs) and ongoing AEs (with onset date before the day of enrollment) at enrollment visit (when done on the same day of EOT or EOS of parent study) will be reported in present study. The Investigator will ask the patient and parents how he/she has felt since the last study visit. To assure the continuing safety of patients in this study, an independent DMC will be responsible for reviewing the safety data on a periodic basis throughout the course of the study as outlined in [Section 6.4](#).

The Investigator should take all appropriate measures to ensure the safety of the patients. Notably, he/she should follow up the outcome of SAEs/AESI until clinical recovery is complete and laboratory results have returned to normal or until progression has been stabilized or death. In all cases, this may imply that observations will continue beyond the last planned visit per protocol, and that additional investigations may be requested by the Sponsor.

When treatment is prematurely discontinued, the patient's observations will continue until the end of the study as defined by the protocol for that patient.

In case of any SAE/AESI with immediate notification brought to the attention of the Investigator at any time after the end of the study for the patient and considered by him/her to be caused by the investigational product with a reasonable possibility, this should be reported to the Sponsor.

Adverse events for each patient will be monitored and documented from the time the subject gives informed consent/assent at Visit 1 until the EOS visit, except for:

- Serious adverse events.
- Adverse events that are ongoing at database lock.

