10.4.1.3 Adverse event of special interest

An adverse event of special interest (AESI) is an AE (serious or nonserious) of scientific and medical concern specific to the Sponsor's product or program, for which ongoing monitoring and immediate notification by the Investigator to the Sponsor is required. Such events may require further investigation in order to characterize and understand them. Adverse events of special interest may be added, modified or removed during a study by protocol amendment.

- Anaphylactic reactions or systemic allergic reactions that are related to IMP and require treatment (refer to [Section 17.5](#) for the definition of anaphylaxis).
- Serious ISRs or severe ISRs that last longer than 24 hours.
Note: A severe ISR (for AE reporting) is any event that meets one of the following criteria:
 - With a diameter of at least 10 cm,
 - Impacting daily activities,
 - With ulceration or necrosis,
 - For which operative intervention is required.
- An infection that meets at least one of the following criteria:
 - Any severe or serious infection (that meet any of the SAE criteria),
 - Is a parasitic infection,
 - Is an opportunistic infection (see list in [Section 17.6](#)).
- Significant elevation of ALT ([Section 17.4](#)):
 - Alanine aminotransferase (ALT) $>3 \times$ the ULN associated with total bilirubin $>2 \times$ ULN; or,
 - Alanine aminotransferase (ALT) $>5 \times$ ULN in patients with enrollment visit ALT $\leq 2 \times$ ULN; or,
 - Alanine aminotransferase (ALT) $>8 \times$ ULN if enrollment visit ALT $>2 \times$ ULN.

- Pregnancy occurring in a female patient entered in the clinical trial or in a female partner of a male patient entered in the clinical trial (It is an unlikely event to happen but for safety concerns, it is imperative to query pregnancy involving a male patient entered in the trial):
 - It will be qualified as an SAE only if it fulfills 1 of the seriousness criteria (see [Section 10.4.1.2](#)),
 - In the event of pregnancy in a female participant, IMP should be discontinued,
 - Follow-up of the pregnancy in a female participant or in a female partner of a male participant is mandatory until the outcome has been determined.
- Symptomatic overdose (serious or nonserious) with IMP/NIMP

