10.4.6 Guidelines for management of specific laboratory abnormalities

Decision trees for the management of certain laboratory abnormalities by Sanofi are provided in [Section 17.4](#).

The following laboratory abnormalities should be monitored, documented, and managed according to the related flow chart in protocol appendices.

- Thrombocytopenia.
- ALT increase.
- Acute renal insufficiency.
- Suspicion of rhabdomyolysis.

In addition, on treatment eosinophil counts >3000 cells/ μ L (3.0 giga/L) are to be reported as AEs.

Table 5 - Summary of adverse event reporting instructions

Adverse event/laboratory abnormality		Reporting timeframe
Serious adverse event		Within 24 hours
Pregnancy		Within 24 hours
Overdose	Symptomatic	Within 24 hours
	Asymptomatic	Routine
ALT elevation	ALT >5 ULN if enrollment visit ALT is ≤ 2 ULN	Within 24 hours
	ALT >8 ULN if enrollment visit ALT is >2 ULN	Within 24 hours
	ALT >3 ULN plus total bilirubin >2 ULN	Within 24 hours
Anaphylactic reactions or acute allergic reactions that require treatment		Within 24 hours
Severe ISR that last longer than 24 hours		Within 24 hours
Serious infections or infections that are AESI (see Section 10.4.1.3 and Section 10.6.3)		Within 24 hours

Abbreviations: AESI = adverse event of special interest; ALT = alanine aminotransferase; ISR = injection site reaction; ULN = upper limit of normal.

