11.4.3.1.2 Adverse event of special interest

The following summaries will be generated:

- Incidence of each AESI will be tabulated.
- The time-to-first event analyzed using Kaplan-Meier (K-M) methods and displayed as K-M plots (cumulative incidence (%)) versus time based on K-M estimates) will be provided to depict the course of onset over time. Number of treatment-emergent AESIs per 100 patient-years (total number of events adjusted for the total duration of exposure) will be presented by decreasing incidence of PT.
- An overview summary of the number (%) of patients with:
 - Any TEAE,
 - Any serious AE (regardless of treatment-emergent status),
 - Any treatment-emergent SAE,
 - Any AE leading to death,
 - Any TEAE leading to permanent study drug discontinuation,
 - Any TEAE by maximum intensity, corrective treatment, and final outcome,
 - Cumulative incidence (K-M estimates) up to specified time points.

Adverse event of special interest (AESI) definitions and the method to identify AESIs will be specified in the SAP.

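### Both SAPs identify the hepatic AESI by a MedDRA term search alone, so the count under the protocol's three ALT/bilirubin criteria cannot be read from the planned AESI tables

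*SAP*

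**What the plan says.** Protocol 9.1 lists the additional safety analyses as numbers and percentages of patients. One item is "Adverse events of special interest (AESI) (AESI definition refers to" Section 10.4.1.3. Section 17.7.2.8.3.1 has the same item for the Japan substudy. Section 11.4.3.1.2 adds "Incidence of each AESI will be tabulated", and Section 17.7.2.10.4.3 carries that approach over to Japan.

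Section 10.4.1.3 includes "Significant elevation of ALT" among the AESIs. Table 5 in Section 10.4.6 repeats its three limbs for reporting within 24 hours:

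- "ALT >3 ULN plus total bilirubin >2 ULN"
- "ALT >5 ULN if enrollment visit ALT is" at most 2 ULN
- "ALT >8 ULN if enrollment visit ALT is >2 ULN"

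Main SAP 2.1.4.1, Table 4, has one hepatic row, drug-related hepatic disorder, with the criterion "Drug-related hepatic disorders - Comprehensive search narrow SMQ (20000006". Japan SAP 3.5.2, Table 5, has the same row and criterion. Neither table has another AESI row that refers to ALT or bilirubin. Main SAP 2.1.4.1 says that its AESI criteria are those of the parent study.

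Protocol 11.4.3.1.2 also says that the SAP will specify both the AESI definitions and the method of identifying AESIs.

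**The concern.** The protocol's hepatic AESI is a laboratory event with numeric limits that depend on ALT at the enrollment visit. The SAPs' hepatic AESI is a set of coded terms. The two can differ in both directions. An ALT elevation that meets a limb is counted only if its coded term belongs to the SMQ. A hepatic AE whose term is in the SMQ is counted even if ALT never came near a limb.

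Long-term safety is the primary objective of the main study and a secondary objective in Japan. In the main SAP the hepatic row feeds AESI incidence, events per 100 patient-years and the Kaplan-Meier time to first event. In the Japan SAP it feeds AESI incidence and the any-AESI line of the TEAE overview. A reader who takes these outputs as counts of the event in Protocol 10.4.1.3 would be reading a different quantity. The changes recorded in main SAP 1.5 and 1.6 and in Japan SAP 3.8 do not mention the difference.

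**Working it through.** There is no stated figure to reproduce. The check sets the definitions side by side.

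**Step 1. Map each protocol limb to the planned outputs.**

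| Protocol 10.4.1.3 limb | AESI row, either SAP | Nearest main SAP laboratory output (Appendix A PCSA) |
|---|---|---|
| ALT >3 ULN with total bilirubin >2 ULN | SMQ row, no threshold | ALT ≥3 ULN and total bilirubin ≥2 ULN: a near match, but reported as a laboratory PCSA |
| ALT >5 ULN, enrollment ALT ≤2 ULN | SMQ row, no threshold | ALT ≥5 ULN, without a split at 2 ULN |
| ALT >8 ULN, enrollment ALT >2 ULN | SMQ row, no threshold | No 8 ULN cut; these cases lie inside ALT ≥5 ULN |

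The ALT cuts in Appendix A are 3, 5, 10 and 20 ULN. Main SAP 2.4.5.3 splits PCSA incidence by status at parent-study baseline and at Week 0, as normal/missing or abnormal by the PCSA criterion. For ALT that criterion is ≥3 ULN, so the split falls at 3 ULN and not at 2 ULN.

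**Step 2. Test whether the PCSA tables can isolate the protocol event.** The cases are hypothetical, with bilirubin normal.

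- Case A: enrollment ALT at most 2 ULN, peak 6 ULN. Since 6 > 5, limb 2 is met and this is a protocol AESI.
- Case B: enrollment ALT 2.5 ULN, peak 6 ULN. Since 2.5 > 2, the limit is 8 ULN, and 6 < 8. This is not a protocol AESI.
- Case C: enrollment ALT 2.5 ULN, peak above 8 and below 10 ULN. Limb 3 is met and this is a protocol AESI.

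All three peaks are at least 5 and below 10 ULN, and all three enrollment values are below 3 ULN. When status is taken at Week 0, A, B and C fall in the same PCSA cell, although only A and C are protocol AESIs. The tables contain the protocol cases but cannot separate them.

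**Step 3. Follow a qualifying event into the SMQ row.** Protocol 10.4.3 requires a laboratory abnormality defined as an AESI to be recorded as an AE. Both SAPs code all AEs in MedDRA and then search them. Cases A and C therefore reach the data being searched, and are counted if their coded terms are in SMQ 20000006. The documents do not list the SMQ's terms, so capture can be neither confirmed nor ruled out.

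**Step 4. Follow a sub-threshold event.** Take a hepatic AE with peak ALT between 3 and 5 ULN and normal bilirubin, recorded because it meets another 10.4.3 criterion, such as having symptoms. It meets no limb. It still enters the hepatic AESI row if its term is in the SMQ.

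**Step 5. Check Japan.** Japan SAP 3.5.3.1 uses the PCSA list in effect at database lock and does not print the ALT cuts. Whether its laboratory tables come any closer to the limbs cannot be established.

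**The case against.** The strongest reply is that the protocol delegated this choice. Section 11.4.3.1.2 hands the SAP the AESI definitions as well as the method, and main SAP 2.1.4.1 discloses that it uses the parent-study criteria. That is a reasonable choice for a rollover study presented by parent-study arm. This part stands: the SAPs did what one protocol section allows. It does not remove the conflict, because 9.1 and 17.7.2.8.3.1 point to 10.4.1.3 for the same count, and 10.4.1.3 says that AESIs are changed by protocol amendment.

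A second reply is that little is lost. Qualifying events occurring in the treatment-emergent period remain in the primary endpoint of any TEAE and in the tables by system organ class and preferred term. Main SAP 2.4.5.3 uses central and local results for PCSAs and lists each PCSA patient with the full profile over time, so cases above 5 or 8 ULN can be found one by one. It also allows further liver analysis if necessary. All of this is correct. It makes the event visible in listings but does not produce the tabulated count, rate or time to first event.

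For Japan, 13 participants were enrolled, and screening ALT or AST above 3 ULN is excluded (E 23), so the 8 ULN limb will rarely apply. This limits the practical effect there.

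A reader might infer that the ALT-based AESI is not tabulated as an AESI anywhere. The documents do not support that, because 10.4.3 puts these events into the coded AE data that the SMQ row searches.

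**Conclusion.** The point holds as a mismatch of definitions. Neither SAP's AESI table counts the hepatic AESI by the three limbs of 10.4.1.3, so that count cannot be read from the planned AESI tables. The main SAP's PCSA tables and listings approximate it: closely for the combined ALT and bilirubin limb, and without the needed split at 2 ULN for the other two. One AESI category with three limbs is affected, in both SAPs. How many patients would be classified differently cannot be determined, because that depends on coding and on an SMQ term list that is not given. The change should be made because it is cheap and the output is a safety count that the protocol defines. The primary endpoint of any TEAE is not affected.

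Three stronger readings are not supported:

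- That the hepatic row will match neither the events reported within 24 hours nor those that lead to stopping. A mismatch is possible but not shown.
- That the 8 ULN criterion is absent from every planned table. This can be seen in the main SAP only, since the Japan cuts are not printed.
- That the row beginning "Hypersensitivity narrow SMQ (20000214) and" needs the same repair because it carries no relatedness condition. That row already has a documented medical review for relevant systemic events, and main SAP 2.4.5.1 tabulates possibly drug-related TEAEs separately. An extra line there would be a preference.

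**What to change.** In both SAPs, add a hepatic AESI row derived from central and local laboratory data with the three 10.4.1.3 limbs, using enrollment-visit ALT as the reference. In the main SAP this can be the pre-dose Week 0 value already defined in Section 2.1. State what is done when that value is missing. Reconcile the row with the AE records that Protocol 10.4.3 requires, and list any discrepancy.

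Use the new row for AESI incidence in both SAPs, and for the rate per 100 patient-years and the Kaplan-Meier outputs in the main SAP. Keep the SMQ row as a separate grouping under the other selected AE groupings. Leave the hypersensitivity row as it is.

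Reconcile Protocol 9.1, 10.4.1.3 and 17.7.2.8.3.1 with 11.4.3.1.2, so that one place governs the AESI definition for analysis.

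The cost is SAP wording, one reconciling sentence in the protocol and minor programming on data already collected. No new assessment or visit is needed.

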2.1.4.2 Deaths

The death observation period are per the observation periods defined above.

- Death on-study: deaths occurring during the time from start of treatment in LTS14424 study to the end of the study.
- Death on-treatment: deaths occurring during the treatment-emergent adverse event period.
- Death poststudy: deaths occurring after the end of the study.

2.1.4.3 Laboratory safety variables

Clinical laboratory data consists of blood analysis, including hematology, clinical chemistry, and urinalysis. Clinical laboratory values after conversion will be analyzed into standard international units and standard international units will be used in all listings and tables. Baseline values for clinical laboratory variables will be the original baseline from the parent study.

Blood samples for clinical laboratories will be taken at Visit 1 (Week 0), Visit 3 (Week 4), Visit 5 (Week 12), Visit 8 (Week 24), Visit 9 (Week 36), Visit 10 (Week 52/EOT), Visit 11 (Week 64/EOS) and/or early termination unless otherwise specified. The laboratory parameters will be classified as follows:

- Hematology:
 - **Red blood cells and platelets and coagulation:** erythrocytes, hemoglobin, hematocrit, platelet count,
 - **White blood cells:** leukocytes, with five-part differential count (neutrophils, lymphocytes, monocytes, basophils, eosinophils).
- Clinical chemistry
 - **Metabolism:** glucose, total cholesterol, total protein, creatine phosphokinase (CPK), albumin,
 - **Electrolytes:** sodium, potassium, chloride, bicarbonate,
 - **Renal function:** creatinine, blood urea nitrogen,
 - **Liver function:** alanine aminotransferase (ALT), aspartate aminotransferase (AST), alkaline phosphatase (ALP), total bilirubin.
- Serum Immunoglobulins: Total IgE and antigen-specific IgE.

Urine samples will be collected as follows:

- **Urinalysis** - include pH, glucose, ketones, leukocyte esterase, blood, protein, nitrate, urobilinogen and bilirubin (by dipstick). If any parameter on the dipstick is abnormal, further urine test is under Investigator's judgement. Testing is performed at Visit 1 (Week 0), Visit 5 (Week 12), Visit 8 (Week 24), Visit 10 (Week 52/EOT), Visit 11 (Week 64/EOS) and/or early termination.
- **Pregnancy test:** A urine pregnancy test must be negative at Visit 1 of present study for enrolling girls who have commenced menstruating, and a urine dipstick pregnancy test will be performed at subsequent onsite visits prior to administration of IMP.

Technical formulas are described in [Section 2.5.1](#).

